5. SUBJECT SELECTION AND WITHDRAWAL

5.1. Subject Recruitment: We plan to recruit a sample of 130 cancer survivors from across the Atlantic provinces (Newfoundland and Labrador, Prince Edward Island, Nova Scotia, and New Brunswick) who completed chemotherapy and/or radiation treatment at least 6 months prior to enrollment (for non-hematological malignancies) and completed cancer treatments including transplant, chemotherapy and/or immunotherapy at least 6 months prior to study entry (for hematological malignancies). We are confident in our ability to recruit the proposed sample. Newfoundland and Labrador has the highest age standardized incidence rate for cancer in Canada. [36] All of the oncologists providing cancer care at Eastern Health (including Co-ls Drs. [name] and [name]) are highly committed to the successful completion of this study. Because we are recruiting cancer survivors at least 6 months after completion of cancer treatment, we will have a large pool of participants to draw from. The primary means of recruitment will be selfreferral; however, we will also employ creative strategies that have been successfully used in previous studies to recruit local participants including: identification of patients with sleep problems through the Personal Well-being Checklist, a distress screening initiative used by the Dr. H. Bliss Murphy Cancer Centre; posting announcements and pamphlets available in the main areas of cancer centres and other areas where eligible patients may frequent; notification of treating physicians across areas (e.g., medical oncology, radiation oncology, hematology oncology, general oncology), nurses and allied health professionals; having new patients consent to be contacted at a later date; notification of community support groups and posting of information on websites frequented by patients; media releases for local newspapers and television programs; paid advertising in print media, on the radio, television and/or internet; and posting advertisements on Kijiji, Buy and Sell, and Classifieds. A key recruitment method to ensure we can make patients across the province and Atlantic Canada aware of the study opportunity is to mail study invitation letters to patients through the Newfoundland and Labrador provincial cancer registry and the Atlantic Path study. Recruitment via the cancer registry will be conducted with the approval and cooperation of the NL Cancer Care Registry (NLCCR). Recruitment via the Atlantic Path study will be conducted with the approval and cooperation of Atlantic Path. Eligible patients (defined as any individual with no current evidence of cancer or clinically stable/inactive disease who completed cancer treatment at least 6 months ago) will be identified by registry cancer case and Atlantic Path records and mailed an invitation letter to participate in the study. The personal information of the individuals eligible for the invitation letter will not be made available to the researchers in this study. Study personnel will provide the stuffed envelopes and the registry or Atlantic Path will be responsible for mailing them, to ensure protection of privacy. Previous studies conducted by the principal investigator have seen successful recruitment through this strategy.

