6. STUDY INTERVENTION

Participants will receive seven individual CBT-I delivered by via video-conferencing over the course of eight weeks. Therapists will be doctoral students in clinical psychology supervised by Drs. [name] and [name]. CBT-I is a manualized multi-component intervention that includes sleep restriction, stimulus control, cognitive restructuring, relaxation training, and sleep hygiene. Sleep restriction is designed to restrict time spent in bed to closely match the time actually spent sleeping. A sleep efficiency percentage (the amount of time spent sleeping divided by the amount of time spent in bed) is calculated, and when the individual is able to achieve 85% sleep efficiency, their sleep time is increased. This process continues until the person can achieve a restful night's sleep with few or no disturbances. Stimulus control is based on the theory that the body eventually becomes conditioned to associate the sleep time and setting with arousal (e.g.

only go to bed when sleepy and refrain from lying awake in bed). This technique is designed to break the perpetuating behaviors and re-associate the bed with sleep. Cognitive restructuring addresses the dysfunctional thoughts and beliefs that serve to maintain and exacerbate insomnia. Individuals are taught to monitor these thoughts and beliefs, challenge their validity, and replace them with adaptive cognitions conducive to the sleep process. Relaxation training targets the physiological and cognitive arousal that accompanies insomnia, and sleep hygiene promotes healthy sleep behaviors and environmental conditions.

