7.3.1. Video-Conference Information

The CBT-I intervention and the assessments will take place over a video conference platform called Zoom (see details about privacy and security below in Section 10). Participants will be given a link to the session via email. At the end of the session the link will expire, and each new Zoom session will generate a new Zoom ID. Participants will be told to not enter their name but to enter their participant number to ensure confidentiality. We previously used telehealth systems embedded in the regional health authorities to conduct these assessments, but patients reported that this was still a barrier to participation because they had to travel (sometimes still quite a distance) to participate in the telehealth meeting. The use of Zoom will allow people to participate from the comfort of their own home and ensure privacy and equal access to treatment for Atlantic Canadians regardless of geography. Treatment sessions will be recorded to assess treatment fidelity and quality assurance.

- **7.4. Follow up Assessments:** Both groups will complete follow up assessments three and six months after completion of treatment to investigate durability of treatment effects.
- **7.5. Randomization:** Participants will be sequentially randomized to one of the two treatment conditions using a 1:1 allocation ratio created by the study biostatistician. The random allocation sequence will be prepared in advance and recorded on sequentially numbered, opaque, sealed and stapled envelopes to be provided to participants in order of study entrance. During the baseline assessment, the research coordinator will inform the participants which group they have been assigned to. All research personnel, including the PI, will be blind to the allocation sequence.

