8.2. Data Analysis Plan

8.2.1. Analysis Plan: To answer our primary research question, we will use mixed-effects models to determine whether treated patients had greater improvements immediately post-treatment (primary endpoint) compared with patients in the control group after their waiting period. Then, data from both groups will be pooled together to assess, with a larger sample size, the durability of any effects observed at 6 months (secondary endpoint). This statistical procedure considers within-subject correlations from repeated measurements in the same subjects and allows estimation of between-group differences without necessitating last observation carried forward or exclusion of participants with missing data. Secondary and exploratory research questions will be answered using mediation/moderation analyses and/or additional mixed effects models.

The primary analyses will occur after the treatment completion (primary endpoint) and durability analyses will occur after the 6-month follow-up (secondary endpoint).

Subsidiary analyses will be conducted to examine the role of sex, gender, and sexual orientation in participant recruitment and retention, pre-treatment symptom severity, as well as the overall efficacy of online CBT-I, and results will be reported separately.

8.2.2. Missing Data: A drawback of any study is the risk of missing data and attrition bias. Our first line of defense will be to minimize the occurrence of missing observations, using a well-constructed study design, well-trained research staff, and acceptable subject burden.^[53] We will decrease barriers to recruitment/retention by scheduling study visits at a convenient time. For those who voluntarily withdraw from the study, we will record their reasons for withdrawing and use this information in a sensitivity analysis. To minimize missing data, all surveys will be checked right after completion. If needed, calls will be made to participants to complete missing data over the phone. For individuals who miss a study visit, RAs will call at least three times (morning/afternoon/evening) over the next week to try rescheduling the assessment.

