Our second line of defense is to apply data analysis strategies that are as robust as possible to data losses. [54] Seeing that no universally accepted method exists for handling missing data, we will initially perform intent-to-treat analyses. We then will perform sensitivity analyses to evaluate the robustness of our results, including compete-case analysis, single imputation methods, such as last-observation and baseline carry forward analyses, and multiple imputation analyses. To avoid reporting bias, we will register our trial with ClinicalTrials.gov and follow the CONSORT recommendations for reporting randomized trials of nonpharmacological interventions. [55]

8.2.3 Sample Size Considerations: Our sample size is based on our primary outcome of PCI using the FACT-Cog immediately post-treatment. Since the primary outcome is continuous, we powered our trial using a t-test to detect the difference between two independent means for score at post-treatment. This is a conservative way to estimate sample size since the longitudinal analysis using the mixed-effects model specified in the analysis plan will provide greater power than a t-test. With power of 0.8 and two-sided alpha of 0.05, we will need at least 62 participants per treatment group and 124 in total to detect an effect size of 0.5.

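### The plan does not say how therapist clustering, present only in the CBT-I arm at the primary endpoint, is handled in the analysis or the sample size

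*Combined protocol and SAP*

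**What the plan says.** Section 6 states who delivers treatment: "Therapists will be doctoral students in clinical psychology supervised by Drs" (two named supervisors follow). Section 4.1 makes the sessions individual and has waitlist participants keep sleep diaries for 8 weeks, with CBT-I only afterwards. The primary comparison in section 8.2.1 sets treated participants just after treatment against controls at the end of their wait (T2 in both schedules). The method is mixed-effects models, described thus: "This statistical procedure considers within-subject correlations from repeated measurements in the same subjects". The two groups are then pooled to assess durability at 6 months.

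Section 8.2.3 gives the sizing: "we powered our trial using a t-test to detect the difference between two independent means for score at post-treatment". The inputs are "With power of 0.8 and two-sided alpha of 0.05", and the result is "we will need at least 62 participants per treatment group and 124 in total" "to detect an effect size of 0.5". Section 5.1 sets the target: "We plan to recruit a sample of 130 cancer survivors".

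The documents do not give the number of therapists, caseloads, how participants are matched to therapists, a therapist ICC or a therapist term. Section 6 does describe manual-based training, weekly supervision with video review, session checklists, and extra supervision when adherence is below 90%. Fidelity data may be examined as moderators if needed.

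**The concern.** Participants treated by the same therapist may have more similar outcomes than participants treated by different therapists. At T2 this can happen in the CBT-I arm but not on the waitlist, so the design is partially nested. A model whose only random effects are for participants, or a t-test on independent observations, counts the treated participants as if each gave fully separate information. If therapists differ in the results they obtain, the standard error of the primary contrast comes out too small, the confidence interval too narrow and the power lower than planned. The same gap recurs in the pooled 6-month analysis, where participants from both arms have been offered CBT-I. Examining fidelity as a moderator does not correct a standard error.

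**Working it through.** **Inputs from the documents.** Two-sided alpha 0.05, power 0.80, effect size d = 0.5, 62 per group (section 8.2.3). Target 130 (section 5.1), allocated "using a 1:1 allocation ratio created by the study biostatistician" (section 7.5), so n = 65 per arm.

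**Assumed inputs.** Number of therapists k from 3 to 10, with equal caseloads; therapist ICC from 0.01 to 0.05, with 0 as the reference. None of these is in the documents.

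**The plan's own figure.** n per arm = 2(1.96 + 0.842)²/0.5² = 62.8, so 63 by the normal approximation and 64 by the t-test. Power at 62 per arm is 0.795 (normal) or 0.789 (t). The stated 62 is reproduced to within one or two participants per arm and is not in dispute on its own inputs.

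**Effect of therapist clustering in one arm.**

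1. Caseload m = 65/k.
2. Design effect in the treated arm: DE = 1 + (m − 1) × ICC. Control arm: 1.
3. True SE of the difference divided by naive SE: R = √((DE + 1)/2).
4. Actual alpha of the test that ignores therapist: 2 × (1 − Φ(1.96/R)).
5. Power at d = 0.5 with the correct SE: approximately Φ(0.5/(R√(2/65)) − 1.96).

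Worked case, k = 3 and ICC 0.05: m = 21.67; DE = 1 + 20.67 × 0.05 = 2.033; R = √(3.033/2) = 1.232; 1.96/1.232 = 1.591; alpha ≈ 0.11.

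| k | ICC | DE | R | Actual alpha | Power, 65 per arm |
|---|---|---|---|---|---|
| any | 0 | 1.000 | 1.000 | 0.050 | 0.813 |
| 10 | 0.01 | 1.055 | 1.014 | 0.053 | 0.803 |
| 8 | 0.01 | 1.071 | 1.018 | 0.054 | 0.800 |
| 4 | 0.01 | 1.153 | 1.037 | 0.059 | 0.785 |
| 3 | 0.01 | 1.207 | 1.050 | 0.062 | 0.774 |
| 10 | 0.05 | 1.275 | 1.067 | 0.066 | 0.762 |
| 8 | 0.05 | 1.356 | 1.085 | 0.071 | 0.747 |
| 4 | 0.05 | 1.763 | 1.175 | 0.095 | 0.679 |
| 3 | 0.05 | 2.033 | 1.232 | 0.11 | 0.639 |

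A simulation of the unadjusted t-test (40,000 runs per setting, k = 4, 6 and 10) agrees with the alpha formula to within about 0.003.

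R is how much larger the true SE is than the naive one. Put the other way, at R = 1.232 the naive SE is understated by 1 − 1/1.232 = 19%.

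**Cost of adjusting.** A simulated analysis of therapist means with Satterthwaite degrees of freedom (65 per arm, d = 0.5) approximates the partially nested model. At ICC 0, power falls from about 0.81 to 0.66–0.69 with 3 therapists, about 0.73–0.74 with 4, and 0.77–0.78 with 8. With 3 therapists and ICC 0.05, power is about 0.48 and alpha is still about 0.065.

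**Pooled 6-month analysis.** If the same k therapists treat all 130 participants, the design effect for a simple pooled mean is 1 + (130/k − 1) × ICC. At k = 4 and ICC 0.05 this is 1 + 31.5 × 0.05 = 2.58, so the true SE is √2.58 = 1.6 times the naive one.

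**The case against.** Four objections carry weight.

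- **The size is unknown.** A reader might infer that there are only a few therapists and that the 5% level is certainly not held. The documents support neither. They give no therapist number and no ICC; with 10 therapists and ICC 0.01 the actual alpha is 0.053, and at ICC 0 it is 0.050. The upper figure needs the smallest assumed k together with the largest assumed ICC.
- **Section 6 works to limit therapist differences.** A reader might take the 90% adherence threshold as an admission that therapists will differ. It is better read as one of several steps to reduce such differences. Those steps may lower the ICC, but the plan does not claim that they bring it to zero.
- **Unspecified is not excluded.** Section 8.2.1 does not write out the random-effects structure, and the quoted sentence explains why mixed models suit repeated and missing data. A therapist term is absent from the text but not ruled out.
- **The alpha argument is narrow.** If CBT-I did nothing for anyone, its delivery by different therapists could not create correlation in outcomes, and the unadjusted test would hold its level. Inflation arises when the average effect is zero but therapists' effects vary. Interval width, power and generalisation to other therapists are therefore the firmer part of the concern.

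Section 8.2.3 also argues that a t-test is a conservative basis for sizing. That covers repeated measures only. Baseline scores remove variance between participants but not variance between therapists, so the effective ICC rises: with an assumed baseline correlation of 0.6, ICC 0.05 becomes 0.05/(1 − 0.36) = 0.078.

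**Conclusion.** The gap holds: there is one-arm nesting by therapist at the primary endpoint, and neither the analysis section nor the sample size says how it is treated. Its consequence is conditional. For any therapist ICC above 0, an analysis without a therapist term gives too small a standard error. With 65 treated, 3 to 10 therapists of equal caseload and ICC 0.01 to 0.05, all assumed except the 65, the true SE is about 1% to 23% larger than the naive one. The actual two-sided alpha is then about 0.053 to 0.11, and power at 65 per arm with the correct SE is about 0.80 down to 0.64 (normal approximation). At ICC 0 nothing changes. This is a worthwhile and inexpensive improvement to the plan; it does not show that the primary result will be invalid.

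**What to change.** Record therapist ID for every treated participant in the analysis data set, and state in the plan the number of therapists, their caseloads and how participants are assigned to them.

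In section 8.2.1, pre-specify a partially nested mixed model: a therapist random effect that applies to the CBT-I arm only up to T2, and to all treated periods in the pooled 6-month analysis. Use Satterthwaite or Kenward-Roger degrees of freedom and report the estimated therapist variance. Make it a pre-specified sensitivity analysis, or the primary model if there are enough therapists to estimate the variance, and fix that choice before outcome data are examined. In section 8.2.3, show power over a range of ICC values.

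The data cost is one variable and one model term. The statistical cost is a wider interval and lower power. With about 8 or more therapists it is small (roughly 0.81 to 0.77–0.78 at ICC 0). With 3 or 4 it is substantial even if therapists do not differ, and the variance itself is poorly estimated, so a mandatory primary random effect would be a real trade-off there.

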
The mail out will include:

NLCCR:

- two letters
 - o a letter from the NLCCR
 - o a letter from the principal investigator
- two brochures
 - one about the NLCCR (http://cancercare.easternhealth.ca/wp-content/uploads/sites/2/2018/02/Cancer-Registry-NLCCR-Brochure_2017-1.pdf)
 - one about our study

Atlantic Path:

- a letter from the principle investigator
- a brochure about our study

Conservative estimates indicate that approximately 15% of patients will be both eligible and interested in participating in our research, yielding 525 potential participants per year. We aim to recruit 1-3 participants per week or approximately 5 participants per month (30 in Year 1 to allow study launch time, 58 in Year 2, and 36 in Year 3). As such, we are more than able to recruit 130 participants in the study period.

Table 1: Study Timeline

TABLE 1	YEAR 1		YEAR 2			YEAR 3			YEAR 4							
Hire/Training																
Treatment Group (n)		7	11	12	14	14	15	15	15	15	6					
Waitlist Group																
Follow Up																
Data Entry/Cleaning																
Data Analysis																
Writing/KT																

5.2. Inclusion Criteria:

5.2.1 For individuals with non-hematological malignancies:

- Men and women who are easily able to understand and read English
- No current evidence of cancer or clinically stable/inactive disease
- Received and completed all adjuvant treatments at least 6 months prior to study entry to allow for neural stabilization and recovery
- Continued maintenance or hormonal therapies are acceptable
- Report PCI as indicated by a score of "quite a lot" or "always" on at least one of the two
 items that assess concentration and memory on the EORTC [1]
- Meet the DSM-5 criteria for insomnia disorder and have a score of 8 or greater on the Insomnia Severity Index^[2]
- Have good performance status as indicated by an ECOG score of 0-2.
- Have high-speed internet connection, webcam, and are fluent using the internet

5.2.2 For individuals with hematological malignancies:

- Men and women who are easily able to understand and read English
- A diagnosis of a hematological malignancy currently in remission.
- Completed cancer treatments including transplant, chemotherapy and/or immunotherapy at least 6 months prior to study entry
- Report PCI as indicated by a score of "quite a lot" or "always" on at least one of the two
 items that assess concentration and memory on the EORTC [1]

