14. AMENDMENTS

May 2023 – Increased sample size to 130 participants; added recruitment of qualitative exit interviews after trial completion.

May 2021 - Added study invitation mailout letters to patients from Atlantic Path study.

Memorial University of Newfoundland

May 30th, 2023

October 2020 – Eligibility criteria adjusted to allow individuals who have finished their cancer treatments 6 months prior to participate; added adverse event questionnaire at mid- and post-treatment.

September 2020 - Removal of participants wearing actigraphy watches (due to COVID-19).

June 2020 – Increased referrals from all Atlantic provinces instead of only Newfoundland and Labrador.

December 2019 – Added new recruitment strategy (local media and newspaper); added treatment fidelity (adherence, competence, etc.) as a component of the trial.

October 2019 – Added eligibility criteria for participants with hematological malignancies.

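### Section 8.2.3 gives 62 per group (124) as the minimum, but its own t-test inputs require 64 (128); the recruitment breakdown also still totals 124 although the target is 130.

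*Combined protocol and SAP*

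**What the plan says.** Section 8.2.3 names the method: "we powered our trial using a t-test to detect the difference between two independent means for score at post-treatment". The inputs are power 0.8, two-sided alpha 0.05 and an effect size of 0.5, and the conclusion is that "we will need at least 62 participants per treatment group and 124 in total to detect an effect size of 0.5". The section calls the t-test a conservative basis because the planned mixed-effects model should be more powerful. It does not mention 130.

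The target elsewhere is 130. The study summary lists 130 participants, and Section 5.1 opens with "We plan to recruit a sample of 130 cancer survivors". Later in 5.1 the yearly plan is "30 in Year 1 to allow study launch time, 58 in Year 2, and 36 in Year 3", and the next sentence concludes that "we are more than able to recruit 130 participants in the study period". Section 14 lists, under May 2023, "Increased sample size to 130 participants", without a statistical reason.

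**The concern.** A sample size section that names its test and gives every input can be checked directly, and this one does not return its stated answer. Section 8.2.3 is also the only sample size justification in the plan, and it supports 124, while the trial is enrolling 130. A reader who takes 124 as the minimum will think that 130 leaves six participants to spare.

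Within 5.1, the yearly breakdown and the conclusion that follows it give different totals, so the reader cannot tell which schedule delivers the current target.

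**Working it through.** **Inputs.** From 8.2.3: two independent means compared by t-test at post-treatment, two-sided alpha 0.05, power 0.80, effect size d = 0.5. I take d as a standardised mean difference, since no SD or raw difference is given. From 7.5: allocation 1:1. From the study summary and 5.1: target 130, or 65 per group.

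**Step 1: the plan's figure by normal approximation.** The formula is n per group = 2 × [(z for 0.975 + z for 0.80) / d]².

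- 2 × [(1.960 + 0.842) / 0.5]² = 62.79 (unrounded z values), which rounds up to 63 per group, 126 in total.
- Power at 62 by the same method: d × √(n/2) = 0.5 × √31 = 2.784, and Φ(2.784 − 1.960) = 0.795. At 63 it is 0.801.

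The stated 62 appears only if 62.79 is rounded down. That is an inference, because the plan shows no working. A one-sided test does not explain it: that gives 50 per group (normal) or 51 (t).

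**Step 2: the exact t-test, which is the test named.** Power is the probability that a noncentral t variable with 2n − 2 degrees of freedom and noncentrality d × √(n/2) falls beyond the two-sided 5% critical values. Solving for power 0.80 gives n = 63.77, so 64 per group, 128 in total.

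| n per group | Total | Exact t-test power at d = 0.5 | d detectable at 80% power |
|---|---|---|---|
| 62 | 124 | 0.789 | 0.507 |
| 63 | 126 | 0.795 | 0.503 |
| 64 | 128 | 0.801 | 0.499 |
| 65 | 130 | 0.808 | 0.495 |

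The shortfall at 62 is 0.800 − 0.789 = 0.011, about one power point.

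**Step 3: the margin in 130.** Against the stated minimum it is 130 − 124 = 6. Against the exact minimum it is 130 − 128 = 2. With 128 analysed (64 and 64) power is 0.801; with 127 (64 and 63) it is 0.798.

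**Step 4: the recruitment breakdown in 5.1.**

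- Yearly figures: 30 + 58 + 36 = 124.
- Table 1 cells: (7 + 11 + 12) + (14 + 14 + 15 + 15) + (15 + 15 + 6) = 30 + 58 + 36 = 124, the same split.
- Gap to the target: 130 − 124 = 6.

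**The case against.** The strongest reply is that nothing practical turns on this. At 62 per group the power of 0.789 and the detectable effect of 0.507 round to the 0.8 and 0.5 that the plan states. A minimum of 124 does not contradict a target of 130, which satisfies it and also exceeds 128. The claim that 130 can be recruited follows an estimate of 525 potential participants a year, so it does not depend on the yearly figures adding up to 130. All of this stands, and it is why the point is minor. It does not make 62 the minimum for the test that the plan names. The expected gain from the mixed model does not do so either: it is offered as a reason why the t-test is conservative, and no correlation or size of gain enters the calculation.

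Three stronger readings are tempting, and the documents do not support them.

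- **That the trial is underpowered.** By its own test it is not: 130 gives 0.808 with complete post-treatment data.
- **That a margin of 2 shows 130 to be too few once dropout is allowed for.** The documents give no loss rate at post-treatment. Section 5.4 lets the principal investigator replace withdrawn participants at discretion, although this does not cover missed visits. Section 8.2.1 plans a model that works "without necessitating last observation carried forward or exclusion of participants with missing data", and 8.2.2 adds retention measures. Any power figure after loss would rest on an assumed rate and would credit the model with nothing.
- **That the recruitment figures as a whole were left out of date.** The headline statements in the study summary and 5.1 do say 130. Only the yearly and Table 1 breakdown, and the derivation in 8.2.3, remain at 124.

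**Conclusion.** Wrong as written, and minor. On the inputs in 8.2.3 the minimum is 64 analysed per group (128), or 63 (126) by normal approximation, and not 62 (124). The error is about one power point (0.789 against 0.80) and the current target absorbs it, since 65 per group gives 0.808. The margin over the correct minimum is 2 participants, before any replacement under 5.4 or any gain from the mixed model. Separately, the derivation and the recruitment breakdown both stop at 124 while the stated target is 130, and no section derives 130 or gives its power.

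These results assume that 0.5 is a standardised difference, that groups are equal in size, and that each participant counted has a post-treatment score.

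**What to change.** 1. In 8.2.3, restate the minimum as 64 analysed per group, 128 in total. Alternatively, name the normal approximation and give 63 and 126.
2. In the same section, state that 130 randomised gives t-test power of 0.808 for an effect size of 0.5 with complete post-treatment data.
3. In 5.1, reconcile the yearly figures and the Table 1 cells with 130, or date-label them as the schedule for 124. Which cells should change is for the sponsor to settle from actual accrual. The increase is listed under May 2023 and the documents give no start date, so a reviewer cannot place the extra six.

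The cost is a text correction. No extra enrolment is needed, and visits and analysis do not change. A table of power under assumed losses is not required.
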